6.5.8 Avelumab: Immune-Related Adverse Events

Because inhibition of PD-L1 stimulates the immune system, avelumab may cause toxicity by increasing the immune response, leading to inflammatory reactions collectively referred to as immune-related adverse events (irAEs).

Immune-related adverse events described with this class of drugs include drugs include dermatitis, pneumonitis, colitis, hepatitis, endocrinopathies including thyroid disorders (hyperthyroidism, hypothyroidism, thyroiditis), adrenal insufficiency, hypophysitis, and diabetes mellitus or hyperglycemia, rash, nephritis and renal dysfunction, encephalitis, eye disorders (including uveitis, iritis), and other immune-mediated reactions including myositis and myocarditis.

Any adverse event which may have an underlying immune-mediated mechanism including those described above, and without other confirmed etiologies, should be considered immune-related and managed according to guidelines described in this section.

Treatment of irAEs is mainly dependent upon severity (NCI CTCAE grade):

- Grades 1 to 2: treat symptomatically or with moderate dose steroids, more frequent monitoring.
- Grades 1 to 2 (persistent): manage similar to high grade AE (Grades 3 to 4).
- Grades 3 to 4: treat with high dose corticosteroids.

For patients receiving avelumab alone, any event suspected to be immune-related should be managed according to the guidance for management of irAEs in this section and Table.

| Gastrointestinal irAEs | | |
|------------------------------------------------------------------------------------------------------------------------------------------------------------------------------------------------------------------------------------------------------------------------------------|----------------------------------------------------------------------------------------------------------------------------------------------------------------------------------------------------------------------------------------------------------|-----------------------------------------------------------------------------------------------------------------------------------------------------------------------------------------------------------------------------------------------------------------------------------------------------------------------------------------------------------------------|
| Severity of Diarrhea/Colitis (NCI-CTCAE v4) | Initial Management | Follow-up Management |
| Grade 1 Diarrhea: <4 stools/day over Baseline Colitis: asymptomatic | Continue avelumab therapy Symptomatic treatment (e.g. loperamide) | Close monitoring for worsening symptoms Educate subject to report worsening immediately If worsens: Treat as Grade 2, 3 or 4. |
| Grade 2 Diarrhea: 4 to 6 stools per day over Baseline; IV fluids indicated <24 hours; not interfering with ADL Colitis: abdominal pain; blood in stool | Withhold avelumab therapy Symptomatic treatment | If improves to Grade I : Resume avelumab therapy If persists >5-7 days or recurs: Treat as Grade 3 or 4. |
| Grade 3 to 4 Diarrhea (Grade 3): ≥7 stools per day over Baseline; incontinence; IV fluids 24 h; interfering with ADL Colitis (Grade 3): severe abdominal pain, medical intervention indicated, peritoneal signs Grade 4: life-threatening, perforation | Withhold avelumab for Grade 3. Permanently discontinue for Grade 4 or recurrent Grade 3. 1.0 to 2.0 mg/kg/day prednisone IV or equivalent Add prophylactic antibiotics for opportunistic infections Consider lower endoscopy | If improves: Continue steroids until Grade ≤ 1, then taper over at least 1 month; resume avelumab therapy following steroids taper (for initial Grade 3). If worsens, persists >3 to 5 days, or recurs after improvement: Add infliximab 5mg/kg (if no contraindication). Note: infliximab should not be used in cases of perforation or sepsis. |
| Dermatological irAEs | | |
| Grade of Rash (NCI-CTCAE v4) | Initial Management | Follow-up Management |
| Grade 1 to 2 Covering ≤30% body surface area | Continue avelumab therapy Symptomatic therapy (for example, antihistamines, topical steroids) | If persists >1 to 2 weeks or recurs: Withhold avelumab therapy |

| | | 
Consider skin biopsy
 
Consider 0.5-1.0 mg/kg/day prednisone or equivalent. Once improving, taper steroids over at least 1 month, consider prophylactic antibiotics for opportunistic infections, and resume avelumab therapy following steroids taper.
 
If worsens: Treat as Grade 3 to 4.
 |
|--------------------------------------------------------------------------------------------------------------------|------------------------------------------------------------------------------------------------------------------------------------------------------------------------------------------------------------------------------------------------------------------------------|---------------------------------------------------------------------------------------------------------------------------------------------------------------------------------------------------------------------------------------------------------------------------------------------------------------|
| Grade 3 to 4 Grade 3: Covering >30% body surface area; Grade 4: Life threatening consequences | 
Withhold avelumab for Grade 3.
 
Permanently discontinue for Grade 4 or recurrent Grade 3.
 
Consider skin biopsy
 
Dermatology consult 1.0 to 2.0 mg/kg/day prednisone or equivalent
 
Add prophylactic antibiotics for opportunistic infections
 | 
If improves to Grade ≤ 1:
 
Taper steroids over at least 1 month; resume avelumab therapy following steroids taper (for initial Grade 3).
 |
| Pulmonary irAEs | | |
| Grade of Pneumonitis (NCI-CTCAE v4) | Initial Management | Follow-up Management |
| Grade 1 Radiographic changes only | 
Consider withholding avelumab therapy
 
Monitor for symptoms every 2 to 3 days
 
Consider Pulmonary and Infectious Disease consults
 | 
Re-assess at least every 3 weeks
 
If worsens:
 
Treat as Grade 2 or Grade 3 to 4.
 |
| Grade 2 Mild to moderate new symptoms | 
Withhold avelumab therapy
 
Pulmonary and Infectious Disease consults
 | 
Re-assess every 1 to 3 days
 
If improves:
 
When symptoms return to Grade ≤ 1, taper steroids
 |

| | | |
|------------------------------------------------------------------------------------------------------------------|----------------------------------------------------------------------------------------------------------------------------------------------------------------------------------------------------------------------------------------------------------------------------------------|------------------------------------------------------------------------------------------------------------------------------------------------------------------------------------------------------------------------------------------------------------------------------------|
| | 
Monitor symptoms daily; consider hospitalization
 
1.0 to 2.0 mg/kg/day prednisone or equivalent
 
Add prophylactic antibiotics for opportunistic infections
 
Consider bronchoscopy, lung biopsy
 | 
over at least 1 month, and then resume avelumab therapy following steroids taper
 
If not improving after 2 weeks or worsening:
 
Treat as Grade 3 to 4.
 |
| Grade 3 to 4 Grade 3: Severe new symptoms; New/worsening hypoxia; Grade 4: Life-threatening | 
Permanently discontinue avelumab therapy.
 
Hospitalize.
 
Pulmonary and Infectious Disease consults.
 
1.0 to 2.0 mg/kg/day prednisone or equivalent
 
Add prophylactic antibiotics for opportunistic infections
 
Consider bronchoscopy, lung biopsy
 | 
If improves to Grade ≤ 1:
 
Taper steroids over at least 1 month
 
If not improving after 48 hours or worsening:
 
Add additional immunosuppression (for example, infliximab, cyclophosphamide, IV immunoglobulin, or mycophenolate mofetil)
 |
| Hepatic irAEs | | |
| Grade of Liver Test Elevation (NCI-CTCAE v4) | Initial Management | Follow-up Management |
| Grade 1 Grade 1 AST or ALT $>3.0 \times$ ULN and/or Total bilirubin $>$ ULN to $1.5 \times$ ULN | Continue avelumab therapy | 
Continue liver function monitoring
 
If worsens:
 
Treat as Grade 2 to 3 or 4.
 |
| Grade 2 AST or ALT >3.0 to $5 \times$ ULN and/or Total bilirubin >1.5 to $3 \times$ ULN | 
Withhold avelumab therapy
 
Increase frequency of monitoring to every 3 days.
 | 
If returns to Grade ≤ 1 :
 
Resume routine monitoring; resume avelumab therapy.
 
If elevation persists >5 to 7 days or worsens:
 
Treat as Grade 3 to 4.
 |

| | | |
|--------------------------------------------------------------------------------------------------------------------------|------------------------------------------------------------------------------------------------------------------------------------------------------------------------------------------------------------------------------------------------------------------------------------------------------------------------------------------------------|------------------------------------------------------------------------------------------------------------------------------------------------------------------------------------------------------------------------------------------------------------------------------------------------------------------------------------------------------|
| 
Grade 3 to 4
 
AST or ALT $>5 \times$ ULN and/or total bilirubin $>3 \times$ ULN
 | 
Permanently discontinue therapy
 
Increase frequency of monitoring to every 1 to 2 days
 
1.0 to 2.0 mg/kg/day prednisone or equivalent
 
Add prophylactic antibiotics for opportunistic infections
 
Consult gastroenterologist/
 
Consider obtaining MRI/CT scan of liver and liver biopsy if clinically warranted
 | 
If returns to Grade ≤ 1:
 
Taper steroids over at least 1 month
 
If does not improve in >3 to 5 days, worsens or rebounds:
 
Add mycophenolate mofetil 1 gram (g) twice daily
 
If no response within an additional 3 to 5 days, consider other immunosuppressants per local guidelines.
 |
| Renal irAEs | | |
| 
Grade of Creatinine Increased
 
(NCI-CTCAE v4)
 | 
Initial Management
 | 
Follow-up Management
 |
| 
Grade 1
 
Creatinine increased $>$ ULN to $1.5 \times$ ULN
 | 
Continue avelumab therapy
 | 
Continue renal function monitoring
 
If worsens:
 
Treat as Grade 2 to 3 or 4.
 |
| 
Grade 2 to 3
 
Creatinine Increased >1.5 and $\leq 6 \times$ ULN
 | 
Withhold avelumab therapy
 
Increase frequency of monitoring to every 3 days
 
1.0 to 2.0 mg/kg/day prednisone or equivalent.
 
Add prophylactic antibiotics for opportunistic infections
 
Consider renal biopsy
 | 
If returns to Grade ≤ 1:
 
Taper steroids over at least 1 month, and resume avelumab therapy following steroids taper.
 
If worsens:
 
Treat as Grade 4.
 |
| 
Grade 4
 
Creatinine increased $>6 \times$ ULN
 | 
Permanently discontinue avelumab therapy
 
Monitor creatinine daily
 | 
If returns to Grade ≤ 1:
 
Taper steroids over at least 1 month.
 |

| | | |
|--|-------------------------------------------------------------------------------------------------------------------------------------------------------------------------------|--|
| | 
1.0 to 2.0 mg/kg/day prednisone or equivalent.
 
Add prophylactic antibiotics for opportunistic infections
 
Consider renal biopsy
 
Nephrology consult
 | |
|--|-------------------------------------------------------------------------------------------------------------------------------------------------------------------------------|--|

Cardiac irAEs

| Myocarditis | Initial Management | Follow-up Management |
|-------------------------------------------------------------------------------------------------------------------------------------------------------------------------------------|----------------------------------------------------------------------------------------------------------------------------------------------------------------------------------------------------------------------------------------------------------------------------------------------------------------------------------------------------------------------------------------------------------------------------------------------------------------------|------------------------------------------------------------------------------------------------------------------------------------------------------------------------------------------------------------------------------------------------------------------------------------------------------|
| New onset of cardiac signs or symptoms and / or new laboratory cardiac biomarker elevations (e.g. troponin, CK-MB, BNP) or cardiac imaging abnormalities suggestive of myocarditis. | 
Withhold avelumab therapy.
 
Hospitalize.
 
In the presence of life threatening cardiac decompensation, consider transfer to a facility experienced in advanced heart failure and arrhythmia management.
 
Cardiology consult to establish etiology and rule-out immune-mediated myocarditis.
 
Guideline based supportive treatment as per cardiology consult*.
 
Consider myocardial biopsy if recommended per cardiology consult.
 | 
If symptoms improve and immune-mediated etiology is ruled out, restart avelumab therapy.
 
If symptoms do not improve/worsen, viral myocarditis is excluded, and immune-mediated etiology is suspected or confirmed following cardiology consult, manage as immune-mediated myocarditis.
 |
| Immune-mediated myocarditis | 
Permanently discontinue avelumab.
 
Guideline based supportive treatment as appropriate as per cardiology consult*.
 
1.0 to 2.0 mg/kg/day prednisone or equivalent
 
Add prophylactic antibiotics for opportunistic infections.
 | 
Once improving, taper steroids over at least 1 month.
 
If no improvement or worsening, consider additional immunosuppressants (e.g. azathioprine, cyclosporine A).
 |

*Local guidelines, or eg. ESC or AHA guidelines

ESC guidelines website: <https://www.escardio.org/Guidelines/Clinical-Practice-Guidelines>

AHA guidelines website:

<http://professional.heart.org/professional/GuidelinesStatements/searchresults.jsp?q=&y=&t=1001>

| Endocrine irAEs | | |
|---------------------------------------------------------------------------------------------------------------------------------------------|-----------------------------------------------------------------------------------------------------------------------------------------------------------------------------------------------------------------------------------------------------------------------------------------------------------------------------------------------------------------------------------------------------------|-----------------------------------------------------------------------------------------------------------------------------------------------------------------------------------------------------------------------------------------------------------|
| Endocrine Disorder | Initial Management | Follow-up Management |
| Grade 1 or Grade 2 (hypothyroidism, hyperthyroidism, adrenal insufficiency, type I diabetes mellitus) | 
Continue avelumab therapy
 
Endocrinology consult if needed
 
Start thyroid hormone replacement therapy (for hypothyroidism), anti-thyroid treatment (for hyperthyroidism), corticosteroids (for adrenal insufficiency) or insulin (for Type I diabetes mellitus) as appropriate.
 
Rule-out secondary endocrinopathies (i.e. hypopituitarism / hypophysitis)
 | 
Continue hormone replacement/suppression and monitoring of endocrine function as appropriate.
 |
| Grade 3 or Grade 4 endocrinopathies (hypothyroidism, hyperthyroidism, adrenal insufficiency, type I diabetes mellitus) | 
Withhold avelumab therapy
 
Consider hospitalization
 
Endocrinology consult
 
Start thyroid hormone replacement therapy (for hypothyroidism), anti-thyroid treatment (for hyperthyroidism), corticosteroids (for adrenal insufficiency) or insulin (for type I diabetes mellitus) as appropriate.
 
Rule-out secondary endocrinopathies (i.e. hypopituitarism / hypophysitis)
 | 
Resume avelumab once symptoms and/or laboratory tests improve to Grade ≤ 1 (with or without hormone replacement/suppression).
 
Continue hormone replacement/suppression and monitoring of endocrine function as appropriate.
 |

| | | |
|------------------------------------------------------------------|--------------------------------------------------------------------------------------------------------------------------------------------------------------------------------------------------------------------------------------------------------------------------------------------------------------------------------------------------------------------------------------------------------------------------------------------------------------------------------------------------------------------------------------------------------------------------------------------------------------------------------------------------------------------------------------------------------------------------------------------------------------------------------------------------------------------------------------------------------------------------------------------------------------------------------------------------------------------------------------------------------------------------|-------------------------------------------------------------------------------------------------------------------------------------------------------------------------------------------------------------------------------------------------------------------------------------------------------------------------------------------------------------|
| Hypopituitarism/Hypophysitis (secondary endocrinopathies) | 
If secondary thyroid and/or adrenal insufficiency is confirmed (i.e. subnormal serum FT4 with inappropriately low TSH and/or low serum cortisol with inappropriately low ACTH):
 
 Refer to endocrinologist for dynamic testing as indicated and measurement of other hormones (FSH, LH, GH/IGF-1, PRL, testosterone in men, estrogens in women) Hormone replacement/suppressive therapy as appropriate Perform pituitary MRI and visual field examination as indicated 
If hypophysitis confirmed:
 
Continue avelumab if mild symptoms with normal MRI. Repeat the MRI in 1 month
 
Withhold avelumab if moderate, severe or life-threatening symptoms of hypophysitis and/or abnormal MRI. Consider hospitalization. Initiate corticosteroids (1 to 2 mg/kg/day prednisone or equivalent) followed by corticosteroids taper during at least 1 month.
 
Add prophylactic antibiotics for opportunistic infections.
 | 
Resume avelumab once symptoms and hormone tests improve to Grade ≤ 1 (with or without hormone replacement).
 
In addition, for hypophysitis with abnormal MRI, resume avelumab only once shrinkage of the pituitary gland on MRI/CT scan is documented.
 
Continue hormone replacement/suppression therapy as appropriate.
 |
|------------------------------------------------------------------|--------------------------------------------------------------------------------------------------------------------------------------------------------------------------------------------------------------------------------------------------------------------------------------------------------------------------------------------------------------------------------------------------------------------------------------------------------------------------------------------------------------------------------------------------------------------------------------------------------------------------------------------------------------------------------------------------------------------------------------------------------------------------------------------------------------------------------------------------------------------------------------------------------------------------------------------------------------------------------------------------------------------------|-------------------------------------------------------------------------------------------------------------------------------------------------------------------------------------------------------------------------------------------------------------------------------------------------------------------------------------------------------------|

Other irAEs (not described above)

| Grade of other irAEs (NCI-CTCAE v4) | Initial Management | Follow-up Management |
|----------------------------------------|--------------------|----------------------|
|----------------------------------------|--------------------|----------------------|

| | | |
|-----------------------------------------------------------------------------------------------------------------------------------------------------------------------|-----------------------------------------------------------------------------------------------------------------------------------------------------------------------------------------------------------------------------------|---------------------------------------------------------------------------------------------------------------------------------------------------------------------------|
| Grade 2 or Grade 3 clinical signs or symptoms suggestive of a potential irAE | Withhold avelumab therapy pending clinical investigation | If irAE is ruled out, manage as appropriate according to the diagnosis and consider re-starting avelumab therapy If irAE is confirmed, treat as Grade 2 or 3 irAE. |
| Grade 2 irAE or first occurrence of Grade 3 | Withhold avelumab therapy 1.0 to 2.0 mg/kg/day prednisone or equivalent Add prophylactic antibiotics for opportunistic infections Specialty consult as appropriate | If improves to Grade ≤ 1 : Taper steroids over at least 1 month and resume avelumab therapy following steroids taper. |
| Recurrence of same Grade 3 | Permanently discontinue avelumab therapy 1.0 to 2.0 mg/kg/day prednisone or equivalent Add prophylactic antibiotics for opportunistic infections Specialty consult as appropriate | If improves to Grade ≤ 1 : Taper steroids over at least 1 month. |
| Grade 4 | Permanently discontinue avelumab therapy 1.0 to 2.0 mg/kg/day prednisone or equivalent and/or other immunosuppressant as needed Add prophylactic antibiotics for opportunistic infections Specialty consult. | If improves to Grade ≤ 1 : Taper steroids over at least 1 month |
| Requirement for 10 mg per day or greater prednisone or equivalent for more than 12 weeks for reasons other than hormonal replacement for adrenal insufficiency | Permanently discontinue avelumab therapy Specialty consult | |

| | | |
|--------------------------------------------------------------------|--|--|
| Persistent Grade 2 or 3 irAE lasting 12 weeks or longer | | |
|--------------------------------------------------------------------|--|--|

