3. ELIGIBILITY CRITERIA (CHECKLIST FORM A)

3.1 Inclusion Criteria

1. Diagnosis of unresectable HCC confirmed pathologically or made according to American Association for the Study of Liver Diseases (AASLD) practice guideline 2010: patients with cirrhosis of any etiology and patients with chronic hepatitis B (HBV) who may not have fully developed cirrhosis, the presence of liver nodule >1cm and demonstrated in a single contrast-enhanced dynamic imaging [magnetic resonance imaging (MRI)] of intense arterial uptake and “washout” in portal venous and delayed phases.
2. Male or female subjects with age: 18-80 years old
3. Eastern Cooperative Oncology Group (ECOG) performance status score of 0 or 1
4. Tumor size 5-25cm and number of lesions ≤ 3
5. Portal vein involvement (Vp1-3) is allowed: Vp1, presence of a tumor thrombus distal to, but not within, the second-order branches of the portal vein; Vp2, presence of a tumor thrombus in the second-order branches of the portal vein; Vp3, presence of a tumor thrombus in the first-order branches of the portal vein. (32)
6. Child-Pugh liver function class A-B7
7. Liver volume minus intrahepatic GTV >700 cc.
8. Minimal distance from GTV to stomach, duodenum, small or large bowel >1 cm.
9. No prior systemic therapy nor immunotherapy
10. No prior trans-arterial chemo-embolization (TACE)
11. No prior radiotherapy to the liver or selective internal radiation (SIRT)

[figure not shown]
12. Written informed consent obtained for clinical trial participation and providing archival tumor tissue, if available.
13. Subjects with confirmed concomitant HBV infection (defined as HBsAg positive or HBV DNA detectable) that are eligible for inclusion must be treated with antiviral therapy (per local institutional practice) prior to enrollment to ensure adequate viral suppression (HBV DNA <2000 IU/mL), must remain on antiviral therapy for the study duration, and continue therapy for 6 months after the last dose of investigational product(s)
14. At least one measurable lesion according to RECIST v1.1.
15. Adequate organ and marrow function, as defined below:
 - Hemoglobin ≥ 9 g/dL
 - Absolute neutrophil count $\geq 1,500/\mu\text{L}$
 - Platelet count $\geq 75,000/\mu\text{L}$
 - Total bilirubin $\leq 2.0 \times \text{ULN}$
 - ALT $\leq 3 \times \text{ULN}$
 - Albumin ≥ 2.8 g/dL
 - INR ≤ 1.6
 - Calculated creatinine clearance ≥ 45 mL/minute as determined by Cockcroft-Gault (using actual body weight) or 24-hour urine creatinine clearance

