6.3.2 TACE adverse event

Common (60-80%)

Post-embolization syndrome (RUQ pain, nausea, fatigue, fever, ileus and transient raised of liver enzymes), usually self-limiting and recover within 7-10 days

Uncommon side effects (<5%)

Hepatic decompensation, liver abscess, cholecystitis, bile duct injury, gastroduodenal ulceration and renal dysfunction

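### The hepatic irAE table gives conflicting avelumab instructions for AST/ALT above 3.0 x ULN, and its bilirubin resume condition does not fit patients admitted at >1.5 to 2.0 x ULN

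*Protocol*

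**What the plan says.** Protocol section 6.5.8 manages suspected immune-related liver events by a three-row table.

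- Grade 1 is "Grade 1 AST or ALT $>3.0 \times$ ULN and/or Total bilirubin" above ULN and up to 1.5 x ULN, with the action "Continue avelumab therapy". If the event worsens, the site moves to the higher rows.
- Grade 2 is "Grade 2 AST or ALT >3.0 to $5 \times$ ULN and/or Total bilirubin >1.5 to $3 \times$ ULN", with the action "Withhold avelumab therapy". Avelumab resumes on return to Grade 1 or lower. An elevation that persists beyond 5 to 7 days, or worsens, is handled as Grade 3 to 4.
- Grade 3 to 4 is AST or ALT >5 x ULN and/or total bilirubin >3 x ULN. The action is permanent discontinuation with corticosteroids, and the steroid taper starts on return to Grade 1 or lower.

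The introduction to section 6.5.8 limits the table to adverse events that may be immune-mediated and have no other confirmed cause.

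The entry criteria in section 3.1 require "Total bilirubin $\leq 2.0 \times \text{ULN" and ALT no higher than 3 x ULN. They list no limit for AST.

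**The concern.** A management table of this kind has to send each laboratory value to one action. Here the Grade 1 and Grade 2 rows start at the same AST/ALT value and order opposite actions, and nothing in the table says which row prevails. The resume and taper conditions both refer back to Grade 1, so the fault in that cell carries into the rows below it.

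The bilirubin rows do not overlap one another. Their lower withhold limit, however, lies inside the range that section 3.1 accepts at entry, and the hepatic rows make no reference to the patient's own baseline.

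Patient safety and avelumab exposure are at stake. Two investigators could act in opposite ways on the same result and both be following the protocol. The liver is a main safety organ in this trial: avelumab follows TACE and SBRT, and grade 4 or 5 hepatic toxicity is one of the events counted in the stopping rule of section 8.3.

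**Working it through.** The protocol states no figure to reproduce on this point. The check places test values in the rows as printed, then intersects the rows with the entry limits. All values are multiples of ULN.

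**Step 1: AST/ALT.** The printed ranges (section 6.5.8) are Grade 1 >3.0 with no upper limit, Grade 2 >3.0 to 5, and Grade 3 to 4 >5.

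| AST/ALT | Rows met | Actions |
|---|---|---|
| 1.5, 2.5, 3.0 | none | none given |
| 3.5, 5.0 | Grade 1 and Grade 2 | continue; withhold |
| 6.0 | Grade 1 and Grade 3 to 4 | continue; permanently discontinue |

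The whole band >3.0 to 5 meets both the continue and the withhold row. Everything above 5 meets both the continue and the discontinue row. Elevations between 1 and 3.0 meet no row. Read literally, a patient whose ALT falls from 4 to 2.5 leaves Grade 2 without entering any defined lower grade, so it is unclear when the resume condition is met.

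**Step 2: bilirubin within the table.** The printed ranges are Grade 1 >1 to 1.5, Grade 2 >1.5 to 3, and Grade 3 to 4 >3. Each test value above 1 (1.2, 1.5, 1.6, 2.0, 2.5, 3.0, 3.5) falls in exactly one row. There is no overlap.

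**Step 3: table against entry limits.**

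- Bilirubin: eligible is ≤2.0 and Grade 2 is >1.5 to 3. The intersection is >1.5 to 2.0, a band 2.0 − 1.5 = 0.5 x ULN wide.
- ALT: eligible is ≤3 and Grade 2 is >3.0 to 5. The intersection is empty, so the entry mismatch comes from bilirubin.

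**Step 4: following one patient through the rows.** Take an illustrative entry bilirubin of 1.8 and a suspected immune-related hepatic event, which may involve only the enzymes. Avelumab is withheld, the enzymes settle, and bilirubin is back at 1.8. The criteria are joined by and/or, so 1.8 > 1.5 alone keeps the patient in Grade 2. Resumption needs bilirubin ≤1.5, which is 1.8 − 1.5 = 0.3 x ULN below the patient's own entry value (0.3/1.8 = 17%). At the entry limit of 2.0 the required fall is 0.5 x ULN (0.5/2.0 = 25%). If the value stays where it is for more than 5 to 7 days, the persistence clause sends the patient to the Grade 3 to 4 row, whose action is permanent discontinuation.

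**Step 5: is baseline used elsewhere?** The diarrhea rows of the same section count stools relative to baseline. The hepatic rows use absolute multiples of ULN only.

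**The case against.** **The AST/ALT overlap may be a slip in one cell.** The Grade 1 label is doubled in that cell, and bilirubin is given there as a range while AST/ALT has only a lower bound. The order of the rows, and the instruction to move up if the event worsens, show that Grade 1 was meant to lie below Grade 2. Above 5 x ULN, section 6.5.6 also points to discontinuation, because it keeps liver test increases of Grade 3 or higher out of its exception for isolated laboratory values. All of this is fair, and a typing or text-extraction error cannot be excluded. It shows that the cell is probably wrong, but it does not supply the intended range. The bilirubin point does not depend on that cell.

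**Entry limits and on-treatment limits serve different purposes.** That is so, and a difference between them is not by itself a contradiction. A reader might infer that eligible patients already meet a withhold row at baseline. The documents do not support that. Section 6.5.8 applies to suspected immune-related events, and section 7.7.1 describes adverse events as unfavorable, new or worsening findings, so a stable entry bilirubin of >1.5 to 2.0 x ULN is not itself an irAE. Nor can one say that such a patient could never resume. Bilirubin may fall below its entry value, and TACE and SBRT come between entry and the first avelumab dose. What stands is the case in which an event has occurred and the patient has recovered fully to the entry level.

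**Frequency.** A reader might also infer that these ranges will be reached often, since section 6.3.2 lists "transient raised of liver enzymes" under effects seen in 60-80% after TACE and section 6.4.4 puts blood-test changes under 80-90% after SBRT. Neither figure supports this. The first is for post-embolization syndrome as a whole, which usually recovers within 7-10 days. By sections 6.4 and 6.5, avelumab starts at least 21 + 14 = 35 days after TACE, before counting SBRT itself. The second heads a group that includes fatigue and skin irritation and gives no size of enzyme rise. Neither is a rate of AST/ALT >3.0 to 5 x ULN on avelumab.

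**Conclusion.** The point holds on the text as printed, in two parts.

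First, the AST/ALT rows contradict each other. All values above 3.0 x ULN carry two conflicting actions, values from ULN to 3.0 x ULN have none, and the Grade 1 or lower target for resumption and steroid taper is unclear as a result. This rests on the Grade 1 cell being printed in the protocol as it reads here.

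Second, the bilirubin rows do not fit the entry limit for patients admitted at >1.5 to 2.0 x ULN. After a suspected immune-related hepatic event, full recovery to entry level does not satisfy the resume condition, and persistence at that level can lead to the permanent-discontinuation row. This assumes that the rows are applied literally and that bilirubin returns to, but not below, its entry value.

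The number of patients affected cannot be estimated. The documents give neither the share entering in that bilirubin band nor the rate of AST/ALT above 3.0 x ULN on avelumab. The point should be corrected because the conflicting actions concern stopping treatment and the correction is small.

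**What to change.** Check the Grade 1 AST/ALT cell in section 6.5.8 against the source table. Then reconcile the three hepatic rows so that each AST/ALT value falls in exactly one row and the Grade 1 or lower target is defined.

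Reconcile the bilirubin rows with the inclusion limit in section 3.1 by stating how the withhold, resume and persistence conditions apply, after a suspected event, to a patient who entered above 1.5 x ULN.

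The choice of limits and rules belongs to the investigators, and none is proposed here. The cost is wording in one table, issued as a protocol amendment. Sample size and analysis are unaffected.
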